1.0 Introduction and Background

Immunotherapy is rapidly replacing chemotherapy as the most effective treatment for non-small cell lung cancer. Immunotherapy resistance is complex and different factors may be responsible for individual patients with immunotherapy resistant lung cancers. Vitamin A deficiency is associated with increased risk of lung cancer, and this deficiency also has been associated with poor immune system function. Our proposed study seeks to improve immune system function in the neoadjuvant setting by treating patients with vitamin A prior to surgical resection for non-small cell lung cancer. The main endpoints of the study will be to evaluate the development of germinal centers in resected cancers and adjacent lymph nodes, histopathologic responses, and changes in immunologic biomarkers.

Vitamin A deficiency was first observed to reduce immune system function and increase risk of pulmonary infections in the early 1900s. This deficiency later was found to increase lung cancer risk in the 1960s. This observation gave rise to the concept of chemoprevention with the use of vitamin A or its derivatives proposed to reduce lung cancer risk [1]. Two chemically distinct but related classes of compounds were investigated for this purpose: retinoids and carotenoids. Retinoids are compounds that are highly similar to vitamin A (retinol). Retinoids have a single cyclic end group and a hydrophilic side chain. These compounds function by binding to retinoid receptors and altering transcription [2-7]. The molecular weights of retinoid compounds are similar to retinol (mw=286.5 g/mol). Carotenoids are much larger compounds (for beta carotene, mw = 536.9 g/mol) that contain multiple cyclic structures. These compounds do not directly interact with retinoic acid receptors. Certain carotenoids including beta carotene are prodrugs of vitamin A and can be converted to vitamin A through enzymatic cleavage in the intestine although the majority of beta-carotene enters the blood stream unchanged [8]. Carotenoids are felt to produce beneficial effects by serving as antioxidants in addition to functioning as pro-vitamins. Unfortunately, in the presence of tobacco carcinogens, beta-carotene undergoes eccentric cleavage leading to the formation of DNA damaging organic molecules, decreased retinoic acid concentrations in lung tissue [8, 9]. Unexpectedly, these drugs have also been shown to increase the development of epithelial pre-neoplasia [9].

Large clinical chemoprevention studies of retinoid or carotenoid supplementation have been negative with the indication of harm for beta-carotene supplementation in patients who continue to smoke [10-12]. The studies that examined beta-carotene and demonstrated increased risk of lung cancer for high risk populations included CARET and ATBC [11, 12]. Another study specifically examined the effects of the retinoid, retinyl palmitate, which will be used in the current study. In this study, called EUROSCAN, 2592 patients were randomized to receive retinyl palmitate or not and no change in cancer risk was observed for patients receiving retinyl palmitate in the entire population as well as the smoking and non-smoking cohorts [10]. Based on the concerns regarding beta-carotene and the lack of harm observed with retinyl palmitate in EUROSCAN, current practice guidelines recommend that patients who currently smoke should avoid high dose beta-carotene supplements but no such recommendations are made for avoiding vitamin A or retinyl palmitate which will be used in the current study [13].

The doses of retinyl palmitate used in prior chemoprevention studies have been much higher than what is currently recommended as a vitamin supplement. In the EURSOCAN study, patients received 300,000 IU of retinyl palmitate daily for the first year followed by 150,000 IU daily for the second year. To reduce risk of acute toxicity, a fifteen fold lower dose, 10,000 IU, was selected for this study. This dose is recommended for the prevention of vitamin A deficiency and is the upper limit of the current recommended daily intake.

While prior studies dampened enthusiasm in the retinoid chemoprevention field, the use of retinoids for lung cancer treatment has shown some promise particularly in combination with targeted agents. In a prior neoadjuvant study, the non-classical retinoid, bexarotene, demonstrated biological effects on cancer tissues even with a short, one week course of treatment [14]. Vitamin A itself and other classical retinoids are known to have beneficial effects on immune system function, and the effectiveness of vitamin A in combination with PD-1 drugs has not been adequately studied.

Vitamin A and other retinoids function by activating nuclear receptors including retinoic acid receptors (RARs) and retinoid X receptors (RXRs) [3, 6, 7]. Activation of these nuclear receptors leads to transcription of target genes and changes in cellular function. Several lines of evidence support an important role for vitamin A to support immune system function. Vitamin A deficiency increases risk of infections in experimental models. Also, vitamin A supplementation reduces mortality from infectious complications in populations with a high risk of deficiency. Furthermore, vitamin A supplementation has been shown to improve antibody titers in response to vaccination in clinical trials.

The mechanisms through which vitamin A promotes immune system function are complex and involve both B-cell and T-cell mediated effects. The focus of the current study will be to examine changes in B-cell function although T-cell subsets will also be examined. In published studies from preclinical models, retinoid treatment of B-cells has been shown to increase cellular proliferation, improve antibody diversification through somatic hypermutation, and increase immunoglobulin production. In addition, animal models have shown that retinoid treatment increases formation of germinal centers which are critical for B-cell maturation.

Given the opportunities to improve patient outcomes by improving immunologic function, investigation of vitamin A supplementation in patients with lung cancer is an exciting opportunity to investigate an immunologic active treatment with minimal toxicities. Vitamin A treatment side effects can occur following prolonged exposure to very high doses but are extremely uncommon with shorter courses of treatment. Changes in cellular function, however, are quite rapid with target gene expression changes occurring within 24 hours. Increases in germinal center (GC) formation triggered by retinoids are seen in animal models following 6 days of retinoid treatment with measurements performed on day 10 (4 days after completing retinoid treatment) [15]. For this study we will examine a 7-day period of treatment with vitamin A in a window-of -opportunity neoadjuvant setting.

In our study, we will examine clinical outcomes including pathologic response and overall survival. The rational for induction of GC formation improving outcomes arises from an early study of resected lung cancers found that primary lung cancers with GC

formation have lower risk of nodal metastases [16]. Although underpowered for statistical comparison, the risk of relapse and overall survival appeared improved in tumors with GCs in this study as well. These findings suggest that inducing GC formation with vitamin A could lead to improved survival for early stage lung cancer patients.

2.0 Objectives

2.1 Primary Objective

- 2.1.1 To compare the percentage of resected cancers containing germinal centers (GCs) in patients who receive neoadjuvant vitamin A to controls.

2.2 Secondary Objective(s)

- 2.2.1 To compare the abundance of GCs in adjacent lymph nodes in patients who receive neoadjuvant vitamin A to controls.
- 2.2.2 To compare histopathologic responses based on tumor necrosis in lung cancer patients who receive neoadjuvant vitamin A to controls.
- 2.2.3 To compare overall survival of patients who receive neoadjuvant vitamin A to controls.

2.3 Exploratory Objectives

- 2.3.1 To describe immunophenotypic changes of monocytes including myeloid derived suppressor cells (MDSCs) in pre- and post-treatment blood samples.

3.0 Patient Selection

3.1 Inclusion Criteria

- 3.1.1 Patient must be \geq 18 years of age
- 3.1.2 Patients must have either biopsy proven or radiographically suspected non-small cell lung cancer.
- 3.1.3 Patients must have disease in the chest that is felt to be surgically resectable.
- 3.1.4 ECOG performance status of 0-2.
- 3.1.5 Ability to understand and the willingness to sign an IRB-approved informed consent document

3.2 Exclusion Criteria

- 3.2.1 Patients < 18 years of age
- 3.2.2 Women who are pregnant or breast feeding.
- 3.2.3 Patients may not be receiving any other investigational agents for the treatment of NSCLC.
- 3.2.4 Patients may not be taking the following medications: high dose vitamin A supplement (multivitamin supplements prohibited only if vitamin A content is greater than 3,500 IU), bexarotene, alitretinoin, tretinoin, adapalene, isotretinoin, acetretin, doxycycline, minocycline, or demeclocycline,
- 3.2.5 Uncontrolled intercurrent illness including, but not limited to, pancreatitis, ongoing or active infection, symptomatic congestive heart failure, unstable angina pectoris, cardiac arrhythmia, or psychiatric illness/social situations that would limit compliance with study requirements.
- 3.2.6 Hypervitaminosis A – toxic effects of ingesting too much vitamin A

3.3 Inclusion of Women and Minorities

Men and women of all races and ethnicities who meet the above-described eligibility criteria are eligible to participate in this study.

The study consent form will also be provided in Spanish for Spanish-speaking participants. Based on CCCWFU population estimates, we expect approximately 40% of participants to be women. Translating this to our sample size estimate of 180, we plan to enroll at least 48 women. Similarly, we expect approximately 5% of study participants to be Hispanic/Latino (N=6). We plan to enroll at least 15% Black or African American (N=18), no American Indian/Alaska Natives, 5% Asian (N=6). Should we not meet or exceed these estimates, the PI will engage the Cancer Center Health Equity Advisory Group to discuss strategies to enhance recruitment in these target populations.

4.0 Registration Procedures

All patients entered on any CCCWFU trial, whether treatment, companion, or cancer control trial, **must** be linked to a study in EPIC within 24 hours of Informed Consent. Patients **must** be registered prior to the initiation of treatment.

You must perform the following steps in order to ensure prompt registration of your patient:

1. Complete the Eligibility Checklist ([Appendix B](#))
2. Complete the Protocol Registration Form ([Appendix A](#))
3. Alert the Cancer Center registrar by phone, *and then* send the signed Informed Consent Form, Eligibility Checklist and Protocol Registration Form to the registrar, either by fax or e-mail.

Contact Information:

Protocol Registrar [contact]
Protocol Registrar [contact]
Protocol Registrar E-MAIL ([contact])

*Protocol Registration is open from 8:30 AM - 4:00 PM, Monday-Friday.

4. Fax/e-mail ALL eligibility source documents with registration. Patients **will not** be registered without all required supporting documents.

Note: If labs were performed at an outside institution, provide a printout of the results. Ensure that the most recent lab values are sent.

To complete the registration process, the Registrar will:

- assign a patient study number
- register the patient on the study
- assign the patient to treatment arm

5.0 Study Outcomes and Study Measures

5.1 Primary Outcome

5.1.1 Presence/absence of germinal centers (GCs) in resected cancer tissues from patients who receive neoadjuvant vitamin A and controls.

5.2 Secondary Outcomes

5.2.1 Measurement of GCs per unit area in adjacent lymph nodes will be assessed using semi-quantitative designation (high, moderate, low, or absent) in patients who receive neoadjuvant vitamin A and controls.

5.2.2 Pathologic response will be defined by tumor necrosis which will be dichotomized as present or absent in patients who receive neoadjuvant vitamin A and controls.

5.2.3 Overall survival of patients receiving neoadjuvant Vitamin A and in controls.

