7.0 Measurement of Effect

7.1.1 Methods for Pathologic Evaluation

Standard pathologic evaluation will be performed following surgical resection. This evaluation includes measurement of lymph node involvement as well as assessment of histopathologic changes such as necrosis within the tumor. This will be classified as present or absent for the purposes of statistical comparison.

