11.0 Statistical Considerations

11.1 Power and Sample Size

Roughly 35% of lung cancers express germinal centers (GC) with the majority of GCs being detected at the tumor margin. Given our target sample size of n=90 patients per arm, we will have 80% power, using a one-tailed alpha of 0.05, to detect an increase to 53% expressing GCs in the treatment arm, given the expected “background” 35% in the standard-of-care arm. Given the current surgical volume, it is estimated that we will enroll 90 patients per year, so that total accrual will last approximately 2 years.

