11.2 Method of Randomization

Patients will be randomized in a 1:1 ratio to receive the vitamin A treatment intervention or standard of care. Patients will be stratified for randomization based on pre-operative stage (stage 1, 2, or 3).

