11.4 Analysis of secondary objectives

11.4.1 Number of GCs per unit area in lymph nodes will be quantified ordinally only, in mutually exclusive ordered groups of high, moderate, low, or absent. We will examine association between treatment arm and rank order of number of GCs in contingency table analysis using methods that incorporate the ordinal ranking of one of the variables. We will also model the outcome of rank order of number of GCs as a function of treatment arm, age, and stage using ordinal logistic regression. As above we will first examine whether there is a significant

interaction between stage and treatment arm with respect to the outcome, and if so will present findings stratified by stage.

11.4.2 Presence/absence of necrosis will be analyzed in a similar manner as the dichotomous outcome of presence/absence of GCs, described above under 11.3.1.

11.4.3 Overall survival will be estimated in treatment and control groups using standard Kaplan-Meier life table analyses and will also be evaluated in the multivariable setting using Cox proportional hazards modeling, where covariates of age and stage will be included. As described above we will first examine whether the statistical interaction between stage and treatment arm is significant.

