Appendix F – Outcomes Data Collection Form

Instructions: Use this form to collect data related to necrosis and number of germinal centers.

Study Number: _____ PID: _____

Investigator: W. [name]. Date: _____ / _____ / _____

1. Necrosis: Present Not Present
2. Germinal centers in tumor: Present Not Present
 - a. Location:
 - i. Intratumoral _____ (Y/N)
 - ii. At margins _____ (Y/N)
3. Density of germinal centers in lymph nodes:
 High Moderate Low Not Present

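### Tumor necrosis is recorded only as present or absent, so secondary outcome 5.2.2 cannot show a change in its extent; a percent field would be a cheap improvement

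*Combined protocol and SAP*

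**What the plan says.** Objective 2.2.2 reads: "To compare histopathologic responses based on tumor necrosis in lung cancer patients who receive neoadjuvant vitamin A to controls". Section 5.2.2 turns this into an outcome: "Pathologic response will be defined by tumor necrosis which will be dichotomized as present or absent". Section 7.1.1 has necrosis assessed in the routine evaluation of the resected specimen and adds: "This will be classified as present or absent for the purposes of statistical comparison". Appendix F captures it as a tick box, "Necrosis: Present Not Present", with no field for extent. Section 11.4.2 states: "Presence/absence of necrosis will be analyzed in a similar manner as the dichotomous outcome of presence/absence of GCs". That means a contingency table, then logistic regression on arm, stage and age, with the stage-by-arm interaction examined first (11.3.1).

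The comparison is randomized. Section 11.2: "Patients will be randomized in a 1:1 ratio to receive the vitamin A treatment intervention or standard of care", stratified by pre-operative stage.

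The documents give no minimum extent, no percent necrosis, no expected control rate and no power for this outcome. The only power statement, in 11.1, concerns germinal centers (GCs).

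**The concern.** A trace focus and near-complete necrosis receive the same score. If vitamin A enlarged necrosis in tumors that already had some, without creating it in tumors that had none, the outcome would not move. A null result on 2.2.2 would then say nothing about extent, although a reader who sees *pathologic response* may take it to.

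The information would also be missing from the trial dataset. Appendix F holds only the tick, so recovering extent later would mean re-reading specimens.

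The label adds a smaller difficulty. Any necrosis in a control tumor is also counted as a response, although that patient received no study drug. A percentage of responders quoted for one arm alone would therefore include spontaneous necrosis.

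**Working it through.** **1. The plan's own figure.** Section 11.1: "Given our target sample size of n=90 patients per arm, we will have 80% power, using a one-tailed alpha of 0.05", for 35% against 53% with GCs. With p̄ = (p₁ + p₂)/2, the usual formula is

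power = Φ{(d − 1.645·SE₀)/SE₁}, SE₀ = √[2p̄(1 − p̄)/n], SE₁ = √{[p₁(1 − p₁) + p₂(1 − p₂)]/n}.

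Here d = 0.18 and p̄ = 0.44. SE₀ = √(2 × 0.2464/90) = 0.0740 and SE₁ = √(0.4766/90) = 0.0728. Power = Φ[(0.18 − 0.1217)/0.0728] = Φ(0.80) = 78.8%. The stated 80% is reproduced to within 2 points.

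**2. What the present/absent comparison can do for necrosis.** Using the same formula, n and one-sided level (carried over from 11.1 as an assumption), the treatment-arm rate detectable with 80% power is:

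| Assumed control rate | Detectable rate |
|---|---|
| 10% | 23.8% |
| 20% | 36.6% |
| 30% | 48.0% |
| 50% | 68.1% |
| 70% | 85.3% |

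The comparison is therefore usable for presence, with detectable increases of about 14 to 18 points.

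**3. What it does when only extent changes.** If presence is equal in the two arms, d = 0 and SE₀ = SE₁, so power = Φ(−1.645) = 5%. This is the significance level itself. It holds at every background rate and needs no outside figure.

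**4. What recording extent would recover.** This step needs assumptions that the documents do not supply. Extent, where necrosis is present, is taken as Beta(1,4), with mean 1/(1 + 4) = 20% of the tumor. Tumors without necrosis score 0. In the treated arm extent is doubled and presence is unchanged. There are 90 per arm, and a one-sided Wilcoxon rank test at 0.05 stands in, without covariates, for an ordinal model. Simulated power:

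| Assumed background | Present/absent | Rank test on percent |
|---|---|---|
| 10% | about 5% | about 7% |
| 20% | about 5% | about 9% |
| 30% | about 5% | about 13% |
| 50% | about 5% | about 32% |
| 70% | about 5% | about 70% |

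Repeat runs agree to within about 2 points.

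**5. Other patterns of effect, same model.**

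| Scenario | Present/absent | Rank test |
|---|---|---|
| 50% to 60%, extent ×1.5 | 38% | 65% |
| 70% to 80%, extent ×1.5 | 45% | 84% |
| 50% in both arms, extent ×1.5 | about 5% | about 17% |
| 20% to 36.6%, presence only | 80% | 79% |
| 50% to 68%, presence only | 80% | 70% |
| 70% to 85%, presence only | 80% | 56% |

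Neither analysis dominates. The rank test gains when extent moves and background is high. The present/absent test is equal or better when only presence moves.

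**The case against.** A reader might go further and infer that 2.2.2 cannot measure a treatment effect at all, because control tumors can also show necrosis. The documents do not support that. The objective is a between-arm comparison in a 1:1 randomized, stage-stratified trial, analyzed with adjustment for stage and age. Spontaneous necrosis is balanced in expectation, and the control arm is there to estimate it. A higher proportion on vitamin A can be read as an effect on presence.

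A reader might also count the missing pre-treatment necrosis value as a defect. It is not one in a randomized comparison. The primary GC outcome has the same post-resection form. Section 3.1.2 also admits radiographically suspected disease, so some patients may have no pre-treatment tissue to score.

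Three further points for the plan have weight. The definition is open and consistent across sections, so nobody is misled about what was counted. No power is claimed for this secondary outcome, in what Appendix B titles a pilot study. Where necrosis is uncommon, recording percent recovers almost nothing: at 10% background the rank test is barely above 5%.

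These points limit the size of the concern but do not remove it. Under the present definition a change in extent alone cannot register at any background rate.

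**Conclusion.** This is a worthwhile, inexpensive improvement, not a flaw that invalidates the objective. As planned, 2.2.2 validly tests an effect on the presence of necrosis. It has only the significance level (5%) as its power against an effect confined to extent. A null result should therefore not be read as showing no effect on the amount of necrosis.

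The benefit of recording extent is uncertain. Under the doubled-extent model it ranges from negligible at 10% to 30% background (about 7% to 13% power) to substantial at 70% (about 70%). Those figures rest on assumed background rates, an assumed Beta(1,4) distribution, an assumed multiplier and the one-sided 0.05 level borrowed from the primary outcome. The 5% figure for present/absent follows from the definition alone, given a one-sided 0.05 test. The primary analysis is unaffected.

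**What to change.** - **Sections 5.2.2 and 7.1.1, Appendix F:** record percent necrosis of the tumor, as 0–100% or in fixed ordered bands set in advance, from the specimen already being evaluated. Presence or absence can be derived from it.
- **Section 11.4.2:** keep the present/absent analysis as planned. Add an ordinal logistic analysis of extent by arm, adjusted for stage and age. Section 11.4.1 already specifies this model for lymph-node GCs, so no new method is needed.
- **Wording:** report the outcome in both arms and in both analyses as *tumor necrosis*. Keeping *response* for the graded version alone would not help, since percent necrosis in an untreated tumor is no more a response than its presence is.

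The cost is one added field per patient and one further secondary analysis to report. It needs no extra patient procedure.

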5.3 Exploratory Outcomes

5.3.1 Immunophenotypic changes among monocytes including quantification of MDSCs in pre- and post-treatment blood and tissue samples. Peripheral blood samples at 2 time points (before treatment, and after treatment). Treatment Plan

5.3 Study-Related Interventions

	Pre-Study ^a	After completion of Vitamin A	Post-Operative
Informed consent	X		
Demographics	X		
Medical history	X		
Concurrent meds	X		
Physical exam	X		
Vital signs	X	X	
Performance Status	X		
B-HCG ^d	X		
Adverse event evaluation		X	X
Research Blood Draw ^e	X	X	
GC Measurement			X

a: Pre-study requirements listed in table must be completed **within** 28 days prior to registration. The research blood draw should be collected **prior** to starting Vitamin A.
b: Additional monitoring interventions may be done per the treating physician depending on which treatment is being given post-assignment.
c: Alkaline phosphatase, total bilirubin, BUN, calcium, creatinine, SGOT[AST], SGPT[ALT]
d: Serum pregnancy test (women of childbearing potential).
e: This procedure is only applicable for patients who chose to participate in the research blood draw

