5.4 Treatment Administration

Patients who are randomized to receive Vitamin A may start no later than 3 months from the time of registration in a time frame that allows them to have surgery with 10 days of completing treatment Vitamin A treatment. Vitamin A will be administered at 10,000 IU orally for 7 consecutive days. Surgery may occur on the day that the last Vitamin A dose is taken. If surgery is delayed more than 21 days from completing Vitamin A, the patient will be considered non-evaluable and will be replaced.

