6.3 General Concomitant Medication and Supportive Care Guidelines

Patients should receive *full supportive care*, including transfusions of blood and blood products, erythropoietin, antibiotics, antiemetics, etc., as clinically indicated. Anti-inflammatory or narcotic analgesics may be offered as needed. Medications considered necessary for the patient's well-being may be given at the discretion of the investigator, i.e., chronic treatments for concomitant medical conditions, as well as agents required for life-threatening medical problems, etc. The reason(s) for treatment, dosage, and dates of treatment should be recorded on the flow sheets.

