9.2 Vitamin A

Product Description: Vitamin A is provided as retinyl palmitate in 10,000 IU capsules from Major Pharmaceuticals.

Storage:

Vitamin A stock bottles will be purchased and stored in the investigational pharmacy. Temperature conditions will be monitored per standard practice. Unopened vials of Vitamin A are stable until the expiration date indicated on the package when stored at controlled room temperature.

Route of Administration: Oral

Drug Accountability: Patients will be asked to record the time and date of medication self-administration with form attached in Appendix.

Disposal: Dispose through the Institutional waste stream and guidelines.

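### In the visible text, the pregnancy test and drug check are timed to registration and need not be repeated before vitamin A, which may start up to 3 months later (minor safety point)

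*Combined protocol and SAP*

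**What the plan says.** The table in section 5.3 (Study-Related Interventions) marks the B-HCG test, for women of childbearing potential, and the concurrent-medication check in the pre-study column only. Footnote a places the pre-study items within "28 days prior to registration". The same footnote ties one item to exposure instead: the research blood draw must precede vitamin A. Footnote e makes that draw optional.

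Section 5.4 sets the dosing window. Patients randomized to vitamin A "may start no later than 3 months from the time of registration", and must do so "in a time frame that allows them to have surgery with 10 days of completing treatment".

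The two checks serve two exclusions in section 3.2. The first is 3.2.2, "Women who are pregnant or breast feeding". The second is 3.2.4, which begins "Patients may not be taking the following medications" and lists high-dose vitamin A supplements (including multivitamins with more than 3,500 IU), several retinoids and three tetracyclines. Under section 4.0, eligibility is confirmed on the Appendix B checklist submitted for registration.

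**The concern.** An exclusion that protects patients from the study drug is most useful at the moment the drug is given. Here the clock for both checks runs to registration, while exposure may begin up to 3 months later. In between, a woman could become pregnant, or a patient could start a barred drug, and nothing in the visible text obliges anyone to look again before the first capsule.

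The drug list is the more practical half. Section 1.0 describes 10,000 IU as the upper limit of recommended daily intake. The plan already tolerates a multivitamin with up to 3,500 IU on top, so up to 10,000 + 3,500 = 13,500 IU a day from the two products. A barred supplement started after registration would take the total above that. The reassurance about dose therefore leans partly on an exclusion that is not re-checked.

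What is at stake is whether two of the plan's own exclusions still hold at dosing. The germinal-center comparison is not at stake.

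**Working it through.** The protocol states no maximum age for these checks at first dose, so there is no figure of its own to reproduce. The age follows from its timing rules.

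**Inputs**
- Earliest permitted check: 28 days before registration (5.3, footnote a).
- Latest permitted start: 3 months after registration (5.4). Three calendar months span 89 to 92 days, depending on the date.
- Course: 7 consecutive daily doses. Surgery may fall on the day of the last dose (5.4).
- Surgery window: I read the wording in 5.4 as within 10 days of completing treatment.

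**Formulas**, for a first capsule on day s after registration:
- age of a check at first capsule = s to s + 28 days
- last capsule = day s + 6
- surgery = day s + 6 to day s + 16

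| First capsule (day s) | Age of check at first capsule (days) | Surgery (day after registration) |
|---|---|---|
| 0 | 0 to 28 | 6 to 16 |
| 28 | 28 to 56 | 34 to 44 |
| 29 | 29 to 57 | 35 to 45 |
| 89 | 89 to 117 | 95 to 105 |
| 92 | 92 to 120 | 98 to 108 |

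**Permitted maximum.** 28 + 89 = 117 and 28 + 92 = 120, so 117 to 120 days. It needs a check on the first allowed day, a start on the last allowed day, and surgery about 95 to 108 days after registration.

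**Threshold.** From s = 29 the youngest possible check is 29 days old, so every such starter has checks over 28 days old. That corresponds to surgery on day 35 or later. For starts on days 1 to 28 the age lies between 1 and 56 days, depending on when the check was done.

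**Search for a re-check elsewhere**
- 5.3, footnote b: extra monitoring is left to the treating physician.
- 6.3: the reasons for other treatments, and their "dosage, and dates of treatment should be recorded on the flow sheets". This documents a new drug but does not require screening it against 3.2.4 before vitamin A.
- 6.4: treatment stops for certain intercurrent illness, or for changes that the investigator judges unacceptable. No test or review is scheduled.
- Appendix L: records pills given, taken and returned, with no eligibility line.
- Appendix M: only its header is visible.

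**The case against.** The best defence is that the two timing rules are compatible and the plan already has means to deal with changes after registration. Under 6.4 the investigator can stop treatment when the patient's condition changes, and footnote b permits added monitoring suited to the assigned treatment. A recognised pregnancy, or an infection needing a barred antibiotic, could be handled that way. This stands as far as it goes. But both provisions are discretionary and act on what is already known; neither detects an unrecognised pregnancy or a newly started barred drug.

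A second objection is that the extra 28 days may not apply to the drug list, because eligibility is attested on the checklist submitted for registration. On that reading the maximum for the drug list is 89 to 92 days. This is fair, and it leaves the threshold unchanged: a start on day 29 or later still rests on information at least 29 days old.

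A reader might also infer more than the documents support:
- *That checks will typically be about four months old.* 117 to 120 days is what the rules permit. The start is tied to the surgery date, and nothing in the documents suggests that such delays are common.
- *That a given number of patients is affected.* The documents give neither the share of late starters nor the share of women of childbearing potential, so any count would only restate a guess.
- *That the trial has no re-check at all.* Consent pages are absent and Appendix M shows only its header. The statement is confined to the visible text.
- *That 6.3 makes this a timing problem for tetracyclines.* It allows "antibiotics, antiemetics, etc., as clinically indicated" without excepting those barred by 3.2.4, but this applies equally to a patient who starts on day 1. It is a separate drafting point and adds nothing here.

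**Conclusion.** The point holds as a minor safety gap. In the visible text, the pregnancy test and medication check are anchored to registration, and neither must be repeated before the first capsule. The permitted maximum age is 117 to 120 days, or 89 to 92 days for the drug list if the registration checklist is taken as a fresh attestation. Every start on day 29 or later rests on checks over 28 days old.

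The size is small. The course is 10,000 IU for 7 days, a daily dose that section 1.0 says is recommended for preventing deficiency. It is a judgement, not a figure in the protocol, that few women in this population will be of childbearing potential. The primary analysis is unaffected.

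The conclusion rests on three things: calendar months of 89 to 92 days, reading the surgery window as within 10 days, and the absence of a re-check rule in the parts not shown. The change is worth making at the next amendment and gives no reason to pause the trial.

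**What to change.** Extend footnote a of 5.3 for patients assigned to vitamin A only:

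1. For women of childbearing potential, the B-HCG must fall within 28 days before the first capsule, and is repeated only if it would be older.
2. The 3.2.4 drug list is re-checked when vitamin A is dispensed, with one line on the Appendix L log to record it.

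Section 9.2 already provides a natural place for the second step: "Vitamin A stock bottles will be purchased and stored in the investigational pharmacy". Anchoring to the start of vitamin A also follows what footnote a already does for the research blood draw.

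The cost is one clause in the footnote, one line on the log, a brief medication review at dispensing for about 90 patients (180 / 2), and an occasional repeat blood test. Patients who start promptly on a recent test need no new blood draw, and the control arm is untouched. No change to 6.3 is needed for this point.
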